3.6 Treatment assignment and treatment groups

In Part B, it is planned that study participants will be dosed with UCB6114 Q2W at ascending dose levels and TFD/TPI will be administered orally bid. Treatment groups will be defined by each UCB6114 dose level and will be presented in ascending order and labelled in the TFLs as illustrated in [Table 3-2](#).

Table 3-2: Treatment Group Labels

UCB6114 Dose Level	Planned Treatment Group Label
Dose Level 1 (any cohort)	UCB6114 500mg + TFD/TPI SoC
Dose Level 2 (any cohort)	UCB6114 1000mg + TFD/TPI SoC
Dose Level 3 (any cohort)	UCB6114 2000mg + TFD/TPI SoC

UCB6114 dose level will be referred to as 'treatment group' from this point onwards in the SAP and in the TFLs.

3.7 Center pooling strategy

Each study site will contribute to the summaries of data from Part B according to the number of evaluable participants recruited; no separate summaries for each site will be presented.

3.8 Coding dictionaries

Adverse events and medical history will be coded by UCB, using the latest available version of the Medical Dictionary for Regulatory Activities (MedDRA®) (Version 25.1 or higher). The National Cancer Institute Common Terminology Criteria for AEs (Version 5.0) (NCI CTCAE) dictionary will also be used by the investigator to assign CTCAE severity grades to each adverse event (AE) and will be merged with the clinical database to define a CTCAE code and term to be used in the summaries of TEAEs by maximum CTCAE severity grade.

Medications (including prior anti-cancer systemic therapies) will be coded according to the World Health Organization Drug Dictionary (WHODD) (Version SEP/2020). Medical procedures will not be coded.

The versions of the coding dictionaries used will be displayed in the relevant TFLs.

3.9 Changes to protocol-defined analyses

The following changes to the protocol have been incorporated into the SAP:

- Other safety data have not been defined as safety endpoints in the protocol, e.g. clinical laboratory data, vital signs, ECG, echocardiogram, ECOG performance status and physical examination. These have been listed in [Section 2.2.1](#) of the SAP as ‘other safety endpoints’ to support the characterization of the safety profile of UCB6114 and to provide supporting evidence of any measurements that are deemed abnormal and clinically significant and reported as an AE.
- ECOG performance status is defined as an efficacy assessment in Section 9.6.2 of the protocol, however, it will also be assessed from a safety perspective in Part B. The SAP therefore includes ECOG performance status as both a safety endpoint ([Section 2.2.1](#)) and an exploratory efficacy endpoint (changes from Baseline during Part B in [Section 2.2.3](#)).
- Section 9.4.2.1 of the protocol does not explicitly define the analysis set to be used for the antitumor activity endpoints but defines the denominator as the number of treated participants, which matches the protocol definition for the SS in Section 9.1 of the protocol. The SAP has been written to clarify that the PPS will be the primary analysis set for the analysis of the antitumor activity endpoints ([Section 3.5.3](#)) and that the SS will be used for the sensitivity analysis ([Section 3.5.2](#)).

4. STATISTICAL/ANALYTICAL ISSUES

4.1 Adjustments for covariates

Not applicable.

4.2 Handling of dropouts or missing data

There will be no imputation of missing data unless otherwise stated in the sections below.

4.2.1 Pharmacokinetics and pharmacodynamics

The reporting and handling of missing values and values that are BLQ in the TFLs is described in [Section 3.1](#). Zero values will be assumed at the predose timepoint on Day 1 of Cycle 1.

4.2.2 Safety laboratory data

The rules for handling values that are BLQ in the safety laboratory data will be the same as those described for PK data in [Section 3.1](#). Any values above the limit of quantification (ALQ) will be assigned as the value of upper limit of quantification.

4.2.3 Dates and times

Partial dates may be imputed for the following reasons:

- Classification of adverse events (AEs) as treatment-emergent;

- Classification of medications recorded on the concomitant medications log as prior or concomitant;
- Calculation of time since initial diagnosis, time since completion of most recent line of anti-cancer therapy and time since progression/relapse on most recent line of anti-cancer therapy.

Imputed dates will not be shown in the listings; all dates will be displayed as reported in the database.

The following rules will be applied for partial onset/start dates:

- If only the month and year are specified and the month and year of the first dose of UCB6114 is not the same as the month and year of the start date then the 1st of the month will be used, or the date of the Screening visit if this is later (if the latter imputation results in an end date that is earlier than the start date, then the 1st of the month will be used);
- If only the month and year are specified and the month and year of the first dose of UCB6114 is the same as the month and year of the start date, then the date of the first dose of UCB6114 will be used. If this results in an imputed start date that is after the specified end date, then the 1st of the month will be used, or the date of Screening if this is later (if the latter imputation results in an end date that is earlier than the start date, then the 1st of the month will be used). If the imputed date is the same date as the date of the first dose of UCB6114 then, for AEs, the event will be regarded as treatment-emergent. For medications, the medication will be classified as concomitant;
- If only the year is specified, and the year of the first dose of UCB6114 is not the same as the year of the start date then January 01 will be used;
- If only the year is specified, and the year of the first dose of UCB6114 is the same as the year of the start date, then the date of the first dose of UCB6114 will be used. If this results in an imputed start date that is after the specified end date, then January 01, or the date of the Screening visit if this is later will be used (if the latter imputation results in an end date that is earlier than the start date, then January 01 will be used). If the imputed date is the date of the first dose of UCB6114 then, for AEs, the event will be regarded as treatment-emergent. For medications, the medication will be classified as concomitant;
- If the onset/start date is completely missing then the onset/start date will be imputed to the date of first dose of UCB6114 and therefore, for AEs, the event will be regarded as treatment-emergent and, for medications, the medication will be classified as concomitant.

The following rules will be applied to partial end/stop dates:

- If only the month and year are specified, then the last day of the month will be used;
- If only the year is specified, then December 31 of the known year will be used;
- If the stop date is completely unknown, the stop date will not be imputed.

Note that the start date or stop date of a prior medication (partial or otherwise) should not be imputed past the Screening date - 1.

In addition to onset and stop dates, the onset and end times of AEs occurring on the day of UCB6114 infusion will be collected on the eCRF. Onset and end times may also be recorded for other AEs that do not occur on the same day as the UCB6114 infusion. The duration of AEs with onset and end times will be calculated in days and hours:minutes (hh:mm) as:

$$\text{Duration of AE} = \text{End Date and Time} - \text{Onset Date and Time}$$

In cases where only the onset and stop dates are recorded for an AE, the duration of an AE will be calculated in days as:

$$\text{Duration of AE} = (\text{Stop Date} - \text{Onset Date}) + 1$$

Note that for participants who have an AE which starts and stops on the same day, but with only a start time or only a stop time recorded, it will be assumed that their AE started from 00:00 (if no start time is recorded) and ended at 23:59 (if no stop time is recorded) on that day.

If the date of a participant's initial diagnosis is incomplete, it will be imputed to the most recent feasible date for the calculation of time since initial diagnosis as follows:

- If only the day is missing, it will be imputed to the last day of the known month;
- If the day and month are missing, it will be imputed to December 31 in the known year;
- If the date of initial diagnosis is completely missing, then time since initial diagnosis will not be calculated.

The above date imputation rules will be applied to partially missing stop dates of a participant's last prior anti-cancer systemic therapy as well as partially and completely missing dates of progression/relapse on last prior anti-cancer systemic therapy.

In cases where the stop date of a participant's last prior anti-cancer systemic therapy and/or a participant's date of progression on last line of prior anti-cancer systemic therapy is completely missing, the participant's Screening date - 1 will be used in the calculation of the time since completion of most recent line of prior anti-cancer systemic therapy and the time since progression/relapse on most recent line of prior anti-cancer systemic therapy, respectively.

Note that partial dates will not be imputed as a participant's first dose of UCB6114 in the calculation of time since initial diagnosis, time since completion of most recent line of prior anti-cancer systemic therapy and time since progression/relapse on most recent line of prior anti-cancer systemic therapy.

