6.6 Prior and concomitant medications

Prior medications will include any medications that started prior to the date of the first dose of UCB6114. This will include medications that started prior to the first dose of UCB6114 and continued after.

Concomitant medications will include medications with a start date on or after the first dose of UCB6114 and prior to the date of the last dose of UCB6114 + 30 days, and whose stop date is either missing, or on or after the date of the first dose of UCB6114. Any medications with a start date prior to the first dose of UCB6114 and a stop date after, or continued to be ongoing during the study, will also be classified as concomitant medications. Medications with a start date > 30 days after the last dose of UCB6114 will be considered as post-study medications and will not be included in the summaries of concomitant medication.

Any medication that started prior to, and stopped after the first dose of UCB6114 or continued to be ongoing during the study, will be classified as both prior and concomitant.

Any medications with missing start dates will be classified as both prior and concomitant.

Any medications with partially missing dates will be handled as described in [Section 4.2.3](#) to classify them as prior or concomitant provided that a stop date is not present or a stop date is present but prior to the first dose of UCB6114.

All medications (prior, concomitant and post-study) will be listed for the ES. Any prohibited concomitant medications, rescue medications or steroid use will be identified via a medical review and flagged in this listing.

Prior and concomitant medications (per the definitions above) will be summarized for the SS by treatment group and by WHODD Anatomical Main Group [Level 1 term text], Pharmacological Subgroup [Level 3 term text] and PT. The reported term will be included in the listing. Separate summaries will be presented for prior medications and concomitant medications. As per the definitions above, prior medications which continued into the Treatment Period will also be classified as concomitant and will be included in both summaries.

All tabulations will be sorted alphabetically by Level 1 term, alphabetical Level 3 term within Level 1 and decreasing frequency of PT in all study participants.

A glossary of all prior and concomitant medications will be presented for the SS including the Anatomical Main Group (Level 1), Pharmacological Subgroup (Level 3), PT and reported term.

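### The cap on imputed prior-medication dates at Screening date - 1 conflicts with the end-of-period stop rule, and misdates and misclassifies drugs whose partial stop date spans the first dose

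*SAP*

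**What the plan says.** The relevant rules are worded the same way in the Part B and Part C SAPs.

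- **4.2.3, partial stop dates.** "If only the month and year are specified, then the last day of the month will be used". A year-only stop goes to 31 December of that year. For a wholly missing stop: "If the stop date is completely unknown, the stop date will not be imputed".
- **4.2.3, note after the stop rules.** "the start date or stop date of a prior medication (partial or otherwise) should not be imputed past the Screening date - 1".
- **4.2.3, partial start dates.** Some month-and-year starts go to the first of the month, "or the date of the Screening visit if this is later".
- **6.6, definition of prior medication.** Any drug started before the first UCB6114 dose. "This will include medications that started prior to the first dose of UCB6114 and continued after".
- **6.6, drugs spanning the first dose.** "Any medication that started prior to, and stopped after the first dose of UCB6114 or continued to be ongoing during the study" counts as both prior and concomitant.
- **6.6, use of 4.2.3.** Partially dated medications are classified through 4.2.3 "provided that a stop date is not present or a stop date is present but prior to the first dose of UCB6114".

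**The concern.** The note in 4.2.3 reads as if a prior medication were one that ended before the participant entered the study. Section 6.6 uses the term differently: a drug is prior because of when it started, even if it runs on into treatment. Put together, the note forbids an imputed stop later than the day before Screening for drugs that may have been taken after first dose. The stop rule a few lines above requires the last day of the recorded month, or 31 December. No precedence is given.

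At stake is whether such a drug appears in the concomitant-medication summary. Two programmers could follow the text and produce different tables, and one of the two stated rules can generate a stop date that the recorded data rule out.

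**Working it through.** The plan gives no figure to reproduce, so the check applies its rules to dated cases.

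**Inputs.** Rules from 4.2.3 and 6.6 as above; Screening lasts up to 28 days (3.2.3). Illustrative dates, assumed: Screening 20 Feb 2023, first dose 10 Mar 2023 (18 days later), known start 5 Jan 2023.

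**Formulas.** End-of-period stop = last day of the recorded month. Capped stop = the earlier of that date and Screening date - 1, which is 19 Feb 2023. A drug started before first dose is also concomitant if it stopped after first dose or is ongoing.

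| Recorded stop | End-of-period rule | Cap, if applied | What 6.6 does |
|---|---|---|---|
| Apr 2023 | 30 Apr: prior and concomitant | 19 Feb: prior only | A stop is present and not before first dose, so 4.2.3 is not called on; stays in both |
| Mar 2023 | 31 Mar: prior and concomitant | 19 Feb: prior only | Not settled |
| Feb 2023 | 28 Feb: prior only | 19 Feb: prior only | Same class either way |
| Ongoing or unknown | Not imputed | Not imputed | Stays in both |

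The exposed case is the second row, where the recorded stop month contains the first dose. Section 6.6 cannot settle it: whether the stop is before first dose depends on the imputation, and whether the imputation rules apply depends on whether the stop is before first dose. A year-only stop in the year of first dose behaves alike, with 31 December against Screening date - 1. One edge case: if the first dose falls on the last day of the period, the imputed stop equals the first-dose date rather than following it.

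**Impossible dates in the exposed case.**

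1. *Outside the recorded month.* A stop recorded as March 2023 becomes 19 February. More generally, let first dose fall on day k of the stop month, g days after Screening. Screening date - 1 is then day k - g - 1, which falls in an earlier month whenever k ≤ g + 1. Over the 365 possible first-dose days of 2023, weighted equally:

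| g (assumed) | Days affected | Share |
|---|---|---|
| 1 | 12 × 2 = 24 | 6.6% |
| 7 | 12 × 8 = 96 | 26.3% |
| 14 | 12 × 15 = 180 | 49.3% |
| 21 | 12 × 22 = 264 | 72.3% |
| 28 | 11 × 29 + 28 = 347 | 95.1% |

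2. *Before the start.* With a known start of 25 Feb 2023 and stop March 2023, the capped stop of 19 Feb is six days before the start. This happens for any start between Screening and first dose.

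**Plausibility.** With first dose on 10 March, 31 - 10 = 21 of the 31 days of March lie after it. Use after first dose is possible, and likelier than not if all days are equally likely, but it is not known.

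**Start dates.** The start rule can give the Screening date, one day past the cap. The start is before first dose under either rule, so the classification does not change.

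**The case against.** A reader might infer that drugs known to have been taken into the Treatment Period lose their concomitant status, and that every drug started before dosing with a partial stop in or after the first-dose month is affected. The documents do not support that. Section 6.6 keeps drugs that stopped after first dose, or are ongoing, in both categories. It turns to 4.2.3 only when the stop is absent or before first dose, and wholly unknown stops are not imputed. Drugs with a wholly missing start are also safe: "Any medications with missing start dates will be classified as both prior and concomitant". The wider loss would follow only from reading the note without 6.6, or from treating a recorded stop month as no stop date at all, which the SAPs do not say.

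It is also fair to object that little depends on the affected table. No endpoint, TEAE definition or analysis set uses it. Listings show dates as recorded, medical review flags prohibited, rescue and steroid use, and the AE listing names co-suspect medications.

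Both objections stand, and they limit the point to partial stops whose month or year contains the first dose, and to descriptive summaries. They do not remove it. In that case 6.6 gives no answer, and the two 4.2.3 rules give opposite ones.

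**Conclusion.** The note is wrong as written in both SAPs. With 6.6's start-based definition it contradicts the end-of-period stop rule. Where a partial stop month or year contains the first dose, it puts the stop before Screening and makes the drug prior only instead of prior and concomitant. The resulting date can be one the record excludes.

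The effect is confined to the prior/concomitant medication summaries, in practice the concomitant one, since the drug counts as prior under either rule. The number of records affected cannot be derived from the SAPs. The shares above rest on assumed screening-to-dose gaps and an even spread of first-dose days; they describe how often the capped date leaves the recorded month, not how often a drug is misclassified. The conclusion also takes a recorded stop month to be a stop date that is present, which is the natural reading of 6.6 but is not stated. It is worth correcting before programming is final, but it does not threaten the safety conclusions.

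**What to change.** In the Part B and Part C SAPs:

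1. In 4.2.3, restrict the note to medications or therapies whose recorded dates show that they ended before Screening.
2. In 4.2.3, state that an imputed date never leaves the recorded month or year and never precedes the start date.
3. In 6.6, state that a partial stop date counts as present and is imputed by the last-day-of-month/31 December rule before the drug is classified.

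The third change is needed as well as the first two, because it removes the circularity in 6.6.

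The cost is a wording change in two documents and a small change to the classification code. The downside is that a few drugs that in fact stopped early in the first-dose month or year, before dosing, will be counted as concomitant. That errs on the conservative side for a summary of concomitant use.

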6.2 Cancer history

All cancer history data for Part B participants will be listed for the ES. This listing will include date of initial diagnosis, tumor type, TNM Classification of Malignant Tumors (TNM) classifications and stage, Duke's score (participants with colorectal adenocarcinoma only), histological and cytological diagnosis details (as relevant), whether the participant had any metastases and associated anatomical location, and whether the participant had received any prior anti-cancer therapies (including the number of lines of any prior systemic therapies, prior radiation therapies and prior anti-cancer surgeries).

Time since initial diagnosis (calculated in months using date of Screening visit and date of initial diagnosis and multiplying the duration in days by 12/365.25), tumor type, T, N, and M classifications and TNM stage, Duke's score (participants with colorectal adenocarcinoma only), presence of metastases and anatomical location of metastases will be summarized by treatment group and for all study participants based on the SS. In the summaries of categorical variables, percentages will be calculated based on the number of study participants with non-missing data. Further, for the Duke's score, the denominator for the percentage calculation will be the number of study participants with colorectal adenocarcinoma.

Cancer history will be presented by Gastric/GEJ-Cancer and CRC tumor type depending on the number of participants with specific tumor types.

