6.4 Cancer status at Screening

The current cancer status of study participants at entry into Part B of this study will be assessed at the Screening visit and listed for the ES. This listing will include tumor type, T, N and M classifications and TNM stage and Duke's score (participants with colorectal adenocarcinoma only), histological and cytological diagnosis details (as relevant), whether the participant has any metastases and associated anatomical location, whether the tumor is recurrent and whether the participant had relapsed from their last line of anti-cancer therapy.

Tumor type, T, N and M classifications and TNM stage, Duke's score (participants with colorectal adenocarcinoma only), presence of metastases and anatomical location of metastases, and time since relapse on last line of therapy (calculated in days using the date of the Screening visit and date of relapse) will be summarized by treatment group and for all study participants based on the SS. In the summaries of categorical variables, percentages will be calculated based on the number of study participants with non-missing data. Further, for Duke's score, the denominator for the percentage calculation will be the number of study participants with colorectal adenocarcinoma.

Cancer status will be presented by Gastric/GEJ-Cancer and CRC tumor type depending on the number of participants with specific tumor types.

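### Partial diagnosis and relapse dates are imputed to month-end or 31 December with no cap at Screening, so descriptive baseline intervals can come out negative

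*SAP*

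**What the plan says.** Section 4.2.3 states an aim for an incomplete date of initial diagnosis: "it will be imputed to the most recent feasible date for the calculation of time since initial diagnosis as follows". Two rules for partial dates follow. The first is "If only the day is missing, it will be imputed to the last day of the known month"; the second is "If the day and month are missing, it will be imputed to December 31 in the known year". The section then applies these rules to partial stop dates of the last prior systemic therapy and to "partially and completely missing dates of progression/relapse on last prior anti-cancer systemic therapy".

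Three other statements in the same section bear on the point:

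- A cap for medications: "the start date or stop date of a prior medication (partial or otherwise) should not be imputed past the Screening date - 1".
- A substitute value for a therapy stop date or progression date that "is completely missing, the participant's Screening date - 1 will be used in the calculation".
- A note that, for these intervals, a partial date will not be set to the date of first dose.

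The imputed dates feed three baseline intervals. Time since diagnosis (Section 6.2) is "calculated in months using date of Screening visit and date of initial diagnosis". Time since relapse (Section 6.4) is "calculated in days using the date of the Screening visit and date of relapse". Time from progression (Section 6.3) runs to the start of UCB6114. The Part C SAP has the same rules and the same three intervals.

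**The concern.** The aim is the latest feasible date, but neither partial-date rule contains a feasibility limit. A programmer will code the rules, not the aim. None of the other three statements supplies the limit. The cap names medications, and a diagnosis or relapse date is not one. The Screening date - 1 substitute applies only when nothing is known about the date. The first-dose note rules out one particular date, not later ones.

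The rules also do not fit together. A participant with no progression date at all gets Screening date - 1, which is possible. A participant whose relapse year is known and equals the Screening year gets 31 December, which is nearly always after Screening. Knowing more gives an impossible value.

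At stake are the means and minima of the intervals in Sections 6.3 and 6.4 and, in principle, 6.2. Section 3.1 includes both statistics in the standard summary. Section 4.2.3 keeps imputed dates out of the listings, so a reader who sees a negative interval will not see the date that produced it.

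**Working it through.** The plan gives no figure to reproduce. The check applies its rules by date arithmetic. All calendar dates and lags below are assumptions; the rules, the reference dates, the 28-day Screening limit (Section 3.2.3), the 30-day month (Section 6.3) and the group size of 3 to 9 (Section 2.4) come from the SAP.

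**1. Single cases.** Interval = reference date - imputed date.

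| Screening | First dose | Recorded relapse | Imputed | To Screening | To first dose |
|---|---|---|---|---|---|
| 15 May 2023 | not set | 2023 | 31 Dec 2023 | -230 | not computed |
| 12 May 2023 | not set | May 2023 | 31 May 2023 | -19 | not computed |
| 10 Jun 2023 | 24 Jun 2023 | June 2023 | 30 Jun 2023 | -20 | -6 |
| 10 Jun 2023 | 24 Jun 2023 | 2023 | 31 Dec 2023 | -204 | -190 |

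In the last two rows the true relapse is taken as 2 June, so the true intervals are +8 and +22 days.

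**2. When it happens.** The rules were run over every Screening date in 2022-2023, with relapse 7, 14, 30, 60, 90 or 180 days before Screening and first dose 7, 14 or 28 days after it.

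- Day missing, interval to Screening: negative for 73.7% of Screening dates at a 7-day lag, 50.7% at 14 days, and 0% at 30 days or more.
- Day missing, imputed date after first dose, 7-day lag: 50.7%, 27.7% and 0% with first dose 7, 14 and 28 days after Screening.
- Year only, interval to Screening: negative for 97.8% at a 7-day lag, falling to 50.4% at 180 days.
- Year only, imputed date after first dose: from 95.9% (7-day lag, first dose at 7 days) down to 42.7% (180-day lag, first dose at 28 days).

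These are shares of Screening dates, given that the relapse date is partial. They are not the share of participants affected.

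**3. With a cap at Screening date - 1.** In the June example both partial dates become 9 June 2023: +1 day to Screening and +15 to first dose. No imputed partial date can then give a negative interval.

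**4. Effect on a mean.** In the first row the uncapped value is -230 and the capped value +1, a difference of 231 days. One such value shifts the mean of n values by 231/n: 231/3 = 77 days, 231/9 = 25.7 days.

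**5. Effect on the under-1-month category (Section 6.3).** The cap moves only dates imputed on or after the Screening date. With Screening of at most 28 days, such a date is at most 28 days before first dose, or after it. After capping it is at most 28 + 1 = 29 days before first dose. Both are below 30, so the participant is in the same category with or without the cap.

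**The case against.** The intent is plain. The partial-date rules are introduced as giving the latest feasible date, and a relapse that preceded study entry cannot feasibly be dated after Screening. The neighbouring text already uses Screening date - 1 for completely missing dates and for prior medications. A careful programmer might add the limit unprompted. The intervals in Section 6.3 are listed by participant, so a negative value would be visible. This stands as mitigation. It does not supply a rule: the aim is defined by what follows it, and what follows has no limit. The Data Evaluation Meetings in Section 3.4 are described for protocol deviations, not for checking derived baseline intervals.

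A reader might also infer more than the document supports:

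- **That a recent relapse with a partial date always lands after first dose.** It does not. With the day missing, the relapse must fall in the same month as Screening or first dose; with year only, in the same calendar year. With Screening on 12 May, first dose may be as late as 9 June (12 May + 28 days), so an imputed 31 May can precede it.
- **That this will be frequent.** The SAP gives no rate of partial relapse dates, and a recent relapse is unlikely to be known by year alone. No diagnosis-date case was run.
- **That recent relapse is over-counted in the under-1-month category because the cap is missing.** Step 5 shows the count is the same either way. Any pull towards short intervals comes from choosing the latest date.
- **That the last prior therapy stop date is equally uncapped.** Section 3.8 counts prior anti-cancer systemic therapies among medications, so the prior-medication cap plausibly covers it.

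**Conclusion.** The point holds as a gap in the written rules. Followed literally, Section 4.2.3 of both SAPs can impute a partial progression/relapse date after Screening or first dose. Time since relapse (6.4) and time from progression to the start of UCB6114 (6.3) can then be negative. Time since diagnosis (6.2) is exposed in principle, if the diagnosis falls in the month or year of Screening.

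The size per affected value is days to a few weeks with the day missing (-19 and -20 in the examples) and can be several months with year only (-204 and -230). One -230 value in place of +1 shifts a mean of 3 to 9 values by 77 to about 26 days and sets the minimum. How many values are affected is unknown. The statement that category counts do not change rests on Screening staying within 28 days.

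Severity is low. These are descriptive baseline summaries; no safety endpoint, dose-escalation decision or antitumor endpoint depends on them.

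**What to change.** In Section 4.2.3 of both SAPs, add 'or Screening date - 1, if earlier' to each of the two partial-date rules, for initial diagnosis and for progression/relapse. State there that the existing prior-medication cap covers the stop date of the last prior systemic therapy, if that is the intent.

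While the text is open, remove completely missing progression/relapse dates from the sentence that extends the diagnosis rules. Under those rules a completely missing date means no calculation, whereas the next paragraph uses Screening date - 1.

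The cost is one clause and one confirming sentence per SAP, plus one line of code, before database lock. The limit is one the SAP already uses twice, so no new convention is introduced.
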